4.1. Inclusion Criteria

Subjects must meet all of the following inclusion criteria to be eligible for enrollment:

- ____ 4.1.1 Subjects must have Stage IV (metastatic) histology- or cytology-confirmed NSCLC. The tumor type must be confirmed by biopsy but the stage may be based on biopsy or imaging.
- ____ 4.1.2 Subjects must have measurable disease of at least 1.0 cm in greatest dimension in at least 2 previously non-irradiated sites (except for lymph nodes, in which the short-axis dimension must be at least 1.5cm).
- ____ 4.1.3 Subjects must be planned to receive standard of care checkpoint inhibitor immune therapy.
- ____ 4.1.4 Subjects must be age \geq 18 years since lung cancer is uncommon in children and likely to have different biologic properties and response to therapy in this age group.
- ____ 4.1.5 Subjects must have ECOG Performance status 0-2 [See [Appendix A](#)].
- ____ 4.1.6 Subjects must have life expectancy greater than 3 months
- ____ 4.1.7 Subjects must have adequate organ and marrow function as defined below within one month of study entry:
 - Hemoglobin \geq 8.0 g/dL
 - Leukocytes \geq 2,000/mcL
 - Absolute neutrophil count \geq 1,000/mcL
 - Platelet count \geq 50,000/mcL
 - Total bilirubin \leq 3.0 X institutional upper limit of normal, with the exception that patients with Gilbert disease may have a serum bilirubin \leq 6 X upper limit of normal
 - AST (SGOT) and ALT (SGPT) \leq 3 X institutional upper limit of normal (or \leq 5 X institutional upper limit of normal if liver metastases are present)
 - Serum Creatinine \leq 3.0 X institutional upper limit of normal
- ____ 4.1.9 Subjects must have the ability to understand and the willingness to sign a written informed consent document.

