5. TREATMENT PLAN

5.1. Initial Radiation Therapy

5.1.1 Dose-fractionation: The initial course of radiation therapy will be administered in 3 or 5 fractions over 3-21 days, at a recommended dose of 6-12 Gy per fraction for 3 total fractions (total dose 18-36 Gy) or 4-10 Gy per fraction for 5 total fractions (total dose 20-50 Gy). Dose-fractionation schemes with a lower BED will be favored, with the exception of situations in which improved local control to palliate symptoms is also a priority for a given patient. Higher BED regimens may also be considered for larger size tumors and more rapidly growing tumors.

5.1.2 Targeted Site: Visceral metastases or metastases in organs involved in the immune system (e.g. liver, lymph nodes) will be targeted preferentially. If a bone or brain metastasis develops while the patient is enrolled in this trial and requires treatment for palliative purposes, we advise also treating a visceral metastasis.

5.1.3 Radiotherapy Technique: Stereotactic body radiation therapy (SBRT) will be the favored treatment delivery technique due to its high conformality to a target volume and avoidance of organs-at-risk (OAR) of toxicity. Other techniques, like 3-dimensional conformal radiotherapy (3DCRT) and intensity modulated radiation therapy (IMRT), will be permitted with the caveat that the patient will, irrespective of technique, undergo CT simulation for treatment planning using SBRT immobilization devices, undergo daily image guidance to confirm the positioning of the tumor prior to treatment, and the plans must meet standard 3 or 5 fraction SBRT dose constraints to normal tissues. The use of 4D-CT and respiratory motion management for treatment planning and delivery are encouraged as necessary.

5.1.4 Treatment Planning: All patients will undergo CT simulation using SBRT immobilization devices. Target volumes (i.e. GTV, CTV, ITV, PTV) will be delineated at the discretion of the treating physician. In general, minimal or no margin should be added

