11.1.2. Definitions

Evaluable for objective response: Only those patients who have received at least one course of radiation therapy, and have had their disease re-evaluated by imaging at least 4 weeks after initiation of therapy will be considered evaluable for response. These patients will have their response classified according to the definitions stated below.

Immune-Related Response Criteria (irRC)⁴³⁻⁴⁴: Novel criteria for the evaluation of antitumor responses with immunotherapeutic agents, as described in Wolchok *et al.* The patterns of response to immune therapy agents differ from those of cytotoxic therapy in several ways: There may be a transient worsening of disease before stabilization or regression, responses can take months to become apparent and may continue long after completion of the initial therapy, and prolonged periods of stable disease are common. For the purposes of this study, irRC will be used for evaluation of all **non-irradiated** index lesions and the unit of measure will be the sum of the products of the two largest perpendicular diameters (SPD) for all index lesions.

Response Evaluation Criteria in Solid Tumors (RECIST) Version 1.1⁴⁵: Method for the evaluation of antitumor responses to cytotoxic agents, as described by Eisenhauer *et al.* For the purposes of this study, RECIST 1.1 criteria will be used only for the evaluation of **irradiated** lesions and the unit of measure will be the single largest diameter.

Measurable lesions on initial imaging: Measurable malignant lesions on *initial* imaging are defined as those that can be accurately measured in at least one dimension as $\geq 10\text{ mm}$ ($\geq 1.0\text{ cm}$) with CT or PET/CT scan. Lymph nodes will be considered malignant (and thus measurable lesions) if their short axis is $\geq 15\text{ mm}$ ($\geq 1.5\text{ cm}$) by CT scan. All other lesions will be considered non-measurable disease. Bone lesions without a soft

tissue component, leptomeningeal disease, ascites, pleural/pericardial effusions, lymphangitis cutis/pneumonitis, inflammatory breast disease, and abdominal masses (not followed by CT or MRI), are considered non-measurable. Simple cysts are by definition non-malignant and non-measurable, but cystic metastases can be considered as measurable lesions, if they meet the size cutoff of measurability described above. Tumor lesions that are situated in a previously irradiated areas are not considered measurable.

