11.2. Response Criteria

The irRC criteria for assessing systemic disease response (including only non-irradiated lesions) can be seen in the following table:

New, measurable lesions (ie, $\geq 5 \times 5$ mm)	Incorporated into tumor burden
New, non-measurable lesions (ie, $< 5 \times 5$ mm)	Do not define progression (but preclude irCR)
Non-index lesions	Contribute to defining irCR (complete disappearance required)
irCR	Disappearance of all lesions in two consecutive observations at least 4 weeks apart
irPR	$\geq 50\%$ decrease in tumor burden compared with baseline in two observations at least 4 weeks apart
irSD	Neither sufficient decrease in tumor burden to qualify as irPR

	nor sufficient increase in tumor burden to qualify as irPD.
irPD	$\geq 25\%$ increase in tumor burden compared with nadir (at any single time point) in two consecutive observations at least 4 weeks apart.

Examples of irRC overall response³⁷:

Measurable response Index and new, measurable lesions (tumor burden),* %	Nonmeasurable response		Overall response Using irRC
	Non-index lesions	New, nonmeasurable lesions	
↓100	Absent	Absent	irCR [†]
↓100	Stable	Any	irPR [†]
↓100	Unequivocal progression	Any	irPR [†]
↓≥50	Absent/Stable	Any	irPR [†]
↓≥50	Unequivocal progression	Any	irPR [†]
↓<50 to <25↓	Absent/Stable	Any	irSD
↓<50 to <25↓	Unequivocal progression	Any	irSD
≥25↓	Any	Any	irPD [†]

*Decreases assessed relative to baseline, including measurable lesions only (>5 x 5 mm).
†Assuming response (irCR) and progression (irPD) are confirmed by a second, consecutive assessment at least 4 wk apart.

RECIST version 1.1 will be used to assess the local response of irradiated lesions only, taking as reference the baseline largest diameter:

Complete Response (CR)	Disappearance of the irradiated lesion
Partial Response (PR)	$\geq 30\%$ decrease in the single largest diameter of the irradiated lesion
Stable Disease (SD)	Neither sufficient decrease in diameter to qualify as PR nor sufficient increase in diameter to qualify as PD
Progressive Disease (PD)	$\geq 20\%$ increase in the single largest diameter of the irradiated lesion. In addition to the relative increase of 20%, the sum must also demonstrate an absolute increase of at least 5 mm (0.5 cm).

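### Irradiated lymph nodes are graded on largest diameter, with complete response only on disappearance, although the plan defines nodal disease by short axis; their local response can therefore be misclassified

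*Combined protocol and SAP*

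**What the plan says.** **Targets.** Section 5.1.2 states that "metastases in organs involved in the immune system (e.g. liver, lymph nodes) will be targeted preferentially".

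**Nodal disease at entry.** The size requirement in inclusion criterion 4.1.2 applies "except for lymph nodes, in which the short-axis dimension must be at least 1.5cm". Section 11.1.2 uses the same axis for measurability: "Lymph nodes will be considered malignant (and thus measurable lesions) if their short axis is" at least 15 mm.

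**Local response.** Section 11.1.2 names RECIST 1.1 for irradiated lesions and then fixes the measure for this study: "the unit of measure will be the single largest diameter". Section 11.2 prints a category table, "taking as reference the baseline largest diameter":
- CR is "Disappearance of the irradiated lesion".
- Partial response (PR) is a 30% or greater "decrease in the single largest diameter of the irradiated lesion".
- Progression (PD) is an increase of at least 20% that is also at least 5 mm.
- Stable disease (SD) is everything else.

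No row or sentence treats nodes differently.

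**Use.** Local response is assessed under 11.1.1. It is a candidate predictor of systemic response in 1.2 and 13.3, and 13.3 plans a nomogram from the multivariate model.

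**The concern.** One dimension decides whether a node is measurable disease, and another decides whether it responded to radiation. This raises two problems.

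- **CR.** The plan does not call a node malignant below 15 mm short axis, yet after irradiation a node of any visible size falls short of CR.
- **PR, SD and PD.** A node that thins without shortening, or thickens without lengthening, is graded on the dimension that changed least.

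What is at stake is the meaning of local response as a covariate. Section 13.3 enters it alongside irradiated tumor site. A grading error confined to nodal targets would tie those two variables together in a model built on about 33 patients.

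**Working it through.** The plan gives no figure on this point to reproduce. The check applies the 11.2 table to example nodes twice: once on largest diameter, as written, and once on short axis. **All node sizes are assumptions.**

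**Inputs.** From 11.2: PR at −30% or below; PD at +20% or above and +5 mm or more; CR only on disappearance; reference is baseline. From 4.1.2 and 11.1.2: nodal threshold of 15 mm short axis.

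**Formula.** Change = (follow-up − baseline) / baseline, computed separately for each axis.

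| Node, long × short axis (mm) | Largest diameter | Short axis |
|---|---|---|
| A: 25 × 18 → 12.5 × 9 | 12.5/25 − 1 = −50%: PR | 9/18 − 1 = −50%: PR |
| B: 22 × 15 → 18 × 8 | 18/22 − 1 = −18.2%: SD | 8/15 − 1 = −46.7%: PR |
| C: 25 × 18 → 17 × 13.5 | 17/25 − 1 = −32%: PR | 13.5/18 − 1 = −25%: SD |
| D: 25 × 16 → 26 × 22 | 26/25 − 1 = +4%: SD | 22/16 − 1 = +37.5%, +6 mm: PD |
| E: 25 × 16 → 30 × 20 | 30/25 − 1 = +20%, +5 mm: PD | 20/16 − 1 = +25%, +4 mm: SD |

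Section 11.1.1 records to the nearest millimeter. Rounding does not change a grade: 12.5 recorded as 12 or 13 gives −52% or −48%, and 13.5 recorded as 13 or 14 gives −27.8% or −22.2%.

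**Reading the table.**
1. Node A shrinks in proportion and ends at 9 mm short axis, 6 mm under the threshold. Both axes give PR. CR is unavailable only because the node is still visible, so the CR problem does not depend on unequal change.
2. Nodes B and C differ in opposite directions. Largest diameter misses a short-axis response in B and credits one in C that the short axis does not show.
3. Node D is growth that largest diameter does not register.
4. Node E differs because of the 5 mm rule. Under proportional growth, PD needs the larger of 20% and 5 mm divided by the baseline dimension. For 25 × 16 mm that is max(20%, 5/25 = 20%) = 20% on the long axis and max(20%, 5/16 = 31.25%) = 31.25% on the short axis. The short-axis bar stays above 20% until the short axis reaches 25 mm (5/25 = 20%).
5. If both axes shrink in proportion, the 30% PR line gives the same answer on either axis.

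**The case against.** **The plan cites RECIST 1.1, so any nodal provisions in it may apply where the table is silent.** This cannot be settled from the documents. For the choice of axis it is weak, because 11.1.2 and 11.2 both state largest diameter for this study. For CR it is stronger. Even so, the printed table is complete on its face, and a reader following it would require disappearance.

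**An entry threshold need not be the follow-up measure.** This is fair. The 15 mm rule is stated for initial imaging, and the next sentence of 11.1.2 places all other lesions in non-measurable disease, so the plan does not say that a node falling below 15 mm is cleared. For non-irradiated lesions, nodes included, the plan uses the product of two diameters and requires disappearance for irCR. A uniform rule is therefore a possible choice, but the plan does not present it as one for nodes. The point also means that the nodal CR size has to be stated and cannot be inferred from the 15 mm entry value.

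**The consequence is limited.** This stands. The coding of local response is not given; if CR and PR are pooled, the CR problem disappears from the model. Site is available for adjustment. Response rates of 20% to 40% in 33 patients give about 7 to 13 responders (33 × 0.20 = 6.6; 33 × 0.40 = 13.2) against about 14 variables or groups listed in 13.3, so any local-response coefficient will be imprecise on either axis.

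**A nodal rule makes grading depend on site.** This is true, but the definition of measurable disease already does.

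**Stronger readings that the documents do not support.** A reader might infer that nodal local response will be wrong as a rule, or wrong in one direction. Nodes A to E show that it depends on how the axes change, and that PR and PD can err either way. A reader might also infer that the case is common because nodes are preferred targets. Section 5.1.2 gives them as one example, 2.4 states the same preference naming only liver, and no frequency appears anywhere.

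**Conclusion.** The mismatch is real and can be shown from the plan's own text. Irradiated nodes **can** be misclassified for local response. CR is out of reach for any node that regresses below the plan's threshold but stays visible. PR, SD and PD can shift in either direction when the axes change unequally, and PD also through the 5 mm rule.

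The size of the effect cannot be computed, because neither the share of nodal targets nor the pattern of axis change is given; the examples show only that grades can differ. It reaches local response and its role in the response model and nomogram.

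It does not reach the primary response rate. Section 11.2 assesses systemic response on non-irradiated lesions only, and 11.1.2 removes a lesion from the index set once it is irradiated. The two-stage design is likewise unaffected. This is a minor but worthwhile correction.

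**What to change.** In 11.1.2 and 11.2, add a rule for irradiated lymph nodes:
- Grade PR, SD and PD on the short axis, with baseline short axis as the reference.
- Define nodal CR as a stated short-axis size below 15 mm, with the value taken from the RECIST 1.1 criteria the plan already cites.
- Keep largest diameter and disappearance for all non-nodal lesions.

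**Cost.** About two sentences and one recorded measurement per follow-up scan of an irradiated node. The short axis is already needed at baseline to call a node measurable and can be read from the same follow-up images, so no scan or visit is added.

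**Downside.** The 5 mm part of the PD rule would then apply to a smaller dimension, so proportional growth in a node under 25 mm short axis would have to be larger to count as progression. The amended text should say whether the 5 mm rule is kept for nodes.

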11. MEASUREMENT OF EFFECT

11.1. Antitumor Effect

11.1.1. Imaging Modalities

At baseline and follow-up, systemic response (for unirradiated lesions) and local response (for irradiated lesions) will be assessed using FDG-PET/CT (preferred) or CT scan of the chest/abdomen/pelvis. Ideally IV contrast and CT slice thickness $\leq 5\text{mm}$ will be used for either type of study. Images will be acquired according to the standard of care schedule used for patients receiving immune checkpoint therapy, at intervals of 4 months or less after initiation of immune therapy. In the event of an imaging study showing disease progression, a confirmatory scan is recommended at least 4 weeks later to confirm progression. The same method of assessment and technique should be used to characterize each index lesion at baseline and during follow-up. All measurements should be recorded in metric notation and specified to the nearest millimeter. All baseline evaluations should be performed as closely as possible to the beginning of treatment and never more than 4 weeks before the beginning of the treatment. Imaging-based evaluation is preferred to evaluation by clinical examination unless the lesion(s) being followed cannot be imaged but are assessable by clinical exam.

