Measureable lesions on follow-up imaging: Per irRC specifications, new measureable lesions on follow-up imaging will be defined as being $\geq 5 \times 5$ mm in size

Index lesions: All measurable lesions up to a maximum of 10 visceral lesions (≤ 5 per organ) and 5 cutaneous lesions, should be identified as index lesions and recorded and measured at baseline. Target lesions should be selected on the basis of their size (lesions with the longest diameter), be representative of all involved organs, and lend themselves to reproducible repeated measurements. It may be the case that, on occasion, the largest lesion does not lend itself to reproducible measurement in which circumstance the next largest lesion which can be measured reproducibly should be selected. It is preferable to exclude cystic metastases as index lesions if other non-cystic lesions are available. Prior to selecting index lesions a decision should be made on which lesion will receive an initial course of radiation therapy, as this lesion is not eligible to be considered as an index lesion to assess response to immune therapy. If any subsequent course(s) of radiation therapy are given to what was previously considered an index lesion, this lesion will no longer be considered an index lesion for subsequent systemic response assessment. The rationale for this is that including irradiated lesions in response assessment would bias the assessment of a systemic effect.

Tumor Burden: At the baseline tumor assessment, the sum of the products of the two largest perpendicular diameters (SPD) of all index lesions is calculated. At each subsequent tumor assessment, the SPD of the index lesions and of new, measurable lesions are added together to provide the total tumor burden: $\text{Tumor Burden} = \text{SPD}_{\text{index lesions}} + \text{SPD}_{\text{new, measurable lesions}}$.

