11.2.1. Best Overall Response

The best response recorded from the start of the treatment until disease progression/recurrence (taking as reference for progressive disease the smallest measurements recorded since the treatment started). The patient's best response assignment will depend on the achievement of both measurement and confirmation criteria.

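### An index lesion irradiated in a later course leaves the follow-up tumor burden, but no rule takes it out of the baseline or nadir sum, so the irRC comparison as written is unmatched

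*Combined protocol and SAP*

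**What the plan says.** Section 11.1.2 makes most measurable lesions index lesions ("All measurable lesions up to a maximum of 10 visceral lesions", plus up to 5 cutaneous ones). The target of the first radiation course is left out from the start. For the rest, "At the baseline tumor assessment, the sum of the products of the two largest perpendicular diameters (SPD) of all index lesions is calculated". If a later course treats one of them, "this lesion will no longer be considered an index lesion for subsequent systemic response assessment"; the stated reason is to keep irradiated lesions from biasing the measure of systemic effect. Follow-up burden is the SPD of the index lesions plus that of new measurable lesions.

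In section 11.2, irPR is a 50% or greater "decrease in tumor burden compared with baseline in two observations at least 4 weeks apart". irPD is a rise of at least 25% over the nadir, confirmed at least 4 weeks later. Section 11.2.1 counts "The best response recorded from the start of the treatment until disease progression/recurrence" and takes the smallest measurements since the start of treatment as the reference for progression.

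On intent, 11.1.1 says: "At baseline and follow-up, systemic response (for unirradiated lesions) and local response (for irradiated lesions) will be assessed". Section 11.1.2 applies irRC to non-irradiated index lesions, and the irRC table in 11.2 is introduced as covering non-irradiated lesions only.

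Section 5.3 gives patients with stable disease a further course to a lesion not yet irradiated. Section 3.3 sets no maximum number of courses in persistent stable disease.

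**The concern.** The follow-up sum loses the whole area of the treated lesion, while the reference sum appears to keep it. The two sides of the comparison then cover different lesions, and the difference looks like shrinkage. Confirmation does not protect against this, because the same artefact is present at the next scan.

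The situation lies on the planned pathway. A measurable target of a further course will usually be an index lesion, and removals can accumulate. Section 4.1.2 requires measurable disease in only two sites. A patient with one measurable lesion in each has a single index lesion after the first course, and irradiating it leaves none. The literal change is then -100%, and no rule covers it.

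Responses after a second course enter the primary endpoint. Best response runs to progression, and neither 1.1 nor 13.1 sets an end date that excludes them. PFS depends on the same sums. The irRC category also determines further radiation (5.3), and a change in extracranial response triggers the follow-up research blood sample (10.2, note 17). Re-scoring at the end would therefore not undo every consequence of a wrong category.

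**Working it through.** **Inputs.** The irPR and irPD thresholds are from 11.2 and the design from 13.2. The documents give no lesion counts or sizes, so every lesion example below is an assumption.

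**1. The plan's own figures.** Section 13.2 states 18 + 15 = 33 patients, 20% versus 40%, and early termination 0.72. Stopping at 4 or fewer responses of 18, and concluding ineffective at 10 or fewer of 33, gives early termination 0.716 at a 20% rate. The chance of passing is 0.046 at 20% and 0.801 at 40%. The stated figures reproduce under that rule.

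**2. Literal irPR.** Let f be the dropped share of baseline SPD and g the size of the remaining lesions relative to baseline. irPR is scored if (1 - f) × g ≤ 0.5. With unchanged disease (g = 1) this needs f ≥ 0.5. With areas 900 + 400 + 400 and the 900 dropped: 800/1700 - 1 = -52.9%.

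**3. Literal irPD at the first later scan.** If the nadir equals baseline, irPD needs g ≥ 1.25/(1 - f). For k equal lesions with one dropped, f = 1/k:

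| k | Shrinkage of the rest that reads as irPR (matched: 50%) | Growth of the rest needed for irPD (matched: 25%) |
|---|---|---|
| 2 | 0% | 150% |
| 3 | 25% | 87.5% |
| 4 | 33% | 67% |
| 5 | 37.5% | 56% |
| 10 | 44% | 39% |

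One-lesion courses needed to reach -50% with unchanged disease: 1 for k = 1 or 2, 2 for k = 3 or 4, 3 for k = 5 or 6, and 5 for k = 10.

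**4. Direction, index lesions only.** At every past scan the literal sum is at least the matched sum, so the literal baseline and nadir are never below the matched ones. The current sum is the same in both. A matched irPR is therefore also a literal irPR, and a literal irPD is also a matched irPD. The only possible errors are a false irPR and a missed or delayed irPD.

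**5. Limit on hidden growth.** Take A = 9 and B = 9; B is dropped and A grows to 17. Literal: 17/18 - 1 = -5.6%. Matched: 17/9 - 1 = +89%. The 17 becomes the literal nadir, so irPD needs A = 1.25 × 17 = 21.25 instead of 1.25 × 9 = 11.25. The literal nadir cannot exceed the first sum after removal, so from that scan on a further 25% rise always suffices. What is hidden is growth up to that scan.

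**6. Rebuilding the nadir.** Let A be 10, 6, 8 and B be 10, 12, 4, so the sums are 20, 18, 12. B is then irradiated and A reaches 9. Literal: 9/12 - 1 = -25%. Subtracting B's 4 from the old nadir: 9/8 - 1 = +12.5%. Matched, with every earlier sum recomputed: 9/6 - 1 = +50%, which is irPD. Subtraction alone is not enough.

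**7. New measurable lesions.** The removal sentence names only index lesions. Let baseline A be 10 and fall to 4, with an irradiated new lesion of 4. If the new lesion stays in the burden, 8/10 - 1 = -20% (irSD). Without it, 4/10 - 1 = -60% (irPR). Here the literal error hides a response.

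**8. What matching does not solve.** Let A go from 10 to 5 and B from 10 to 12: 17/20 - 1 = -15%, irSD. B is irradiated and A stays at 5. Matched: 5/10 - 1 = -50%, irPR, with no change in A since the irSD scan.

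**9. Effect on the decision.** One patient is 1/33 = 3.03 points. If misclassification added 2, 3 or 5 points to a true 20% rate (assumed values), the chance of passing would rise from 0.046 to 0.082, 0.106 or 0.166.

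**The case against.** The strongest reply is that the documents already mean a matched comparison. Sections 11.1.1, 11.1.2 and 11.2 confine systemic response to non-irradiated lesions, and the reason given for dropping the lesion is to avoid bias. This stands as evidence of intent. A reader might otherwise infer that the sponsor will score these patients wrongly and that the reported response rate will be inflated; the documents do not support that. But intent does not supply the calculation. At baseline the lesion was non-irradiated, so keeping its area there fits the same wording, and nothing says how the nadir is rebuilt.

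A related argument joins two sentences: decreases are assessed against baseline using measurable lesions only (footnote in 11.2), and lesions in previously irradiated areas are not measurable (11.1.2). The second concerns initial imaging, before the lesion was irradiated, so it does not remove the lesion from the baseline sum.

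Section 11.2.3 has all responses reviewed with files and images at study completion, and note 13 in 10.2 records the location of each treated lesion. A reviewer could notice a false irPR. That is a partial safeguard: the reviewer has no stated rule to apply, and the review comes after the treatment decisions in 5.3.

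It is also fair that 13.1 speaks of response after the initial course, which is at least ambiguous about later courses, and that the size of the effect rests on assumptions.

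**Conclusion.** The concern holds as an unmatched calculation that should be fixed. Applied as written, the plan can score unchanged disease as a confirmed irPR once dropped index lesions held at least 50% of baseline SPD. It can also hide progression that occurs up to the first scan after removal.

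Two stronger readings fail. It is tempting to say that the error always favors efficacy. That is true for index lesions, but an irradiated new measurable lesion kept in the burden can hide a response. It is also tempting to put a figure on the inflation of the response rate. The documents give neither lesion counts nor the frequency of such courses, so the 2, 3 and 5 points above are illustrations only. What can be said is that the final rule separates 10 from 11 responders of 33, so a single reclassified patient can matter.

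**What to change.** 1. In 11.1.2, state that after an index lesion is irradiated, the baseline sum, all earlier follow-up sums and hence the nadir are recomputed over the lesions still non-irradiated. The recomputed sums serve later assessments only; categories already assigned stand. State also that an irradiated new measurable lesion leaves all follow-up sums.
2. State that if no index lesion remains, best response is held at the last assessment before that course, and state how progression is then classified for PFS. A percentage change from zero is undefined, so a rule is needed; no particular event rule is prescribed here.
3. Report the response rate using only assessments before any second radiation course as a sensitivity analysis. Matching alone does not stop irSD turning into irPR when a growing lesion is the one removed.

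The cost is a few sentences and a recomputation from lesion measurements already collected. There are three downsides. The observed response rate may be lower than under the literal reading. The percentage change rests on fewer lesions and is noisier. The recomputed nadir can also give irPD from growth that occurred before the removal: with A at 10, 6, 8 and then steady at 8, 8/6 - 1 = +33%.
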